8.2.2 Physical examinations

A complete physical examination will be performed and include an assessment of the following: general appearance, respiratory, cardiovascular, abdomen, lymph nodes and musculoskeletal system.

Physical examination will be performed at timelines as specified in the SoA, Investigators should pay special attention to clinical signs related to previous serious illnesses, new or worsening abnormalities may qualify as adverse events, see Section 8.3.7 for details.

8.2.3 ECG

ECGs are required within 7 days prior to starting study treatment and when clinically indicated.

Twelve-lead ECGs will be obtained after the subject has been rested in a supine position for at least 5 minutes in each case. The Investigator or designated physician will review the paper copies of each of the timed 12-lead ECGs on each of the study days when they are collected.

ECGs will be recorded at 25 mm/sec. All ECGs should be assessed by the investigator as to whether they are clinically significantly abnormal / not clinically significantly abnormal. If there is a clinically significant abnormal finding, the Investigator will record it as an AE on the eCRF. The original ECG traces must be stored in the subject medical record as source data.

8.2.4 Vital signs

- Oral temperature, pulse rate, Respiratory rate and blood pressure will be assessed.
- Blood pressure and pulse measurements will be assessed in sitting position with a completely automated device. Manual techniques will be used only if an automated device is not available.

- Blood pressure and pulse measurements should be preceded by at least 5 minutes of rest for the subject in a quiet setting without distractions (e.g., television, cell phones).
- Vital signs (to be taken before blood collection for laboratory tests) will consist of 1 pulse and 3 blood pressure measurements (3 consecutive blood pressure readings will be recorded at intervals of at least 1 minute). The average of the 3 blood pressure readings will be recorded on the CRF.

8.3 Collection of adverse events

The Principal Investigator is responsible for ensuring that all staff involved in the study are familiar with the content of this section

The definitions of an AE or SAE can be found in Appendix B.

AE will be reported by the subject (or, when appropriate, by a caregiver, surrogate, or the subject's legally authorized representative).

The investigator and any designees are responsible for detecting, documenting, and recording events that meet the definition of an AE or SAE. For information on how to follow/up AEs see section 8.3.3.

8.3.1 Method of detecting AEs and SAEs

Care will be taken not to introduce bias when detecting AEs and/or SAEs. Open-ended and non-leading verbal questioning of the subject is the preferred method to inquire about AE occurrences.

8.3.2 Time - period and frequency for collecting AE and SAE information

Adverse Events will be collected continuously from time of ICF until 28 days after last olaparib dose in Treatment Phase and Follow-up Phase.

All SAEs will be recorded and reported to the sponsor or designee within 24 hours, as indicated in Appendix B. The investigator will submit any updated SAE data to the sponsor within 24 hours of it being available.

Investigators are not obligated to actively seek AE or SAE in former study subjects. However, if the investigator learns of any SAE, including a death, at any time after a subject's last visit and he/she considers the event to be reasonably related to the Study treatment or study participation, the investigator may notify the sponsor.

The method of recording, evaluating, and assessing causality of AE and SAE and the procedures for completing and transmitting SAE reports are provided in Appendix B.

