6.7 Treatment after the end of study (Post Trial Access to Olaparib)

Subjects receiving olaparib at the time of study completion (i.e. after completion of Treatment Phase) may continue to receive olaparib, if in the opinion of their treating physician they are continuing to derive clinical benefit from continued treatment or have not progressed clinically. These subjects shall receive the study drug free of cost under a separate compassionate use program and will not receive the medication via the clinical trial supply for this study. These subjects shall not be actively monitored for AE's and it will be the responsibility of the treating physician to ensure reporting of all SAE's, pregnancies, overdose and medication errors to the relevant authorities as per the standard practice in India.

DISCONTINUATION OF TREATMENT AND SUBJECT WITHDRAWAL

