8.4 Safety reporting and medical management

8.4.1 Reporting of serious adverse events

All SAEs have to be reported, whether or not considered causally related to the study drug, or to the study procedure(s). All SAEs will be recorded in the CRF.

If any SAE occurs in the course of the study, then Investigators or other site personnel inform the appropriate AstraZeneca representatives within one day i.e., immediately but **no later than 24 hours** of when he or she becomes aware of it.

The designated AstraZeneca representative works with the Investigator to ensure that all the necessary information is provided to the AstraZeneca Patient Safety data entry site **within 1 calendar day** of initial receipt for fatal and life-threatening events and **within 5 calendar days** of initial receipt for all other SAEs.

For fatal or life-threatening adverse events where important or relevant information is missing, active follow-up is undertaken immediately. Investigators or other site personnel inform AstraZeneca representatives of any follow-up information on a previously reported SAE within one calendar day i.e., immediately but **no later than 24 hours** of when he or she becomes aware of it.

Once the Investigators or other site personnel indicate an AE is serious in the EDC system, an automated email alert is sent to the designated AstraZeneca representative.

If the EDC system is not available, then the Investigator or other study site staff reports a SAE to the appropriate AstraZeneca representative by telephone.

The AstraZeneca representative will advise the Investigator/study site staff how to proceed.

Investigators or other site personnel send relevant CRF modules by fax to the designated AstraZeneca representative.

For further guidance on the definition of a SAE, see Appendix B of the Clinical Study Protocol.

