8.4.5.3 Management of prolonged hematological toxicities while on study treatment

If a subject develops prolonged haematological toxicity such as:

- ≥ 2 weeks interruption/delay in study treatment due to CTC grade 3 or worse anaemia and/or development of blood transfusion dependence
- ≥ 2 weeks interruption/delay in study treatment due to CTC grade 3 or worse neutropenia (ANC $< 1 \times 10^9/L$)
- ≥ 2 weeks interruption/delay in study treatment due to CTC grade 3 or worse thrombocytopenia and/or development of platelet transfusion dependence (Platelets $< 50 \times 10^9/L$)

Check weekly differential blood counts including reticulocytes and peripheral blood smear. If any blood parameters remain clinically abnormal after 4 weeks of dose interruption, the subject should be referred to haematologist for further investigations. Bone marrow analysis and/or blood cytogenetic analysis should be considered at this stage according to standard haematological practice. Study treatment should be discontinued if blood counts do not recover to CTC gr 1 or better within 4 weeks of dose interruption.

Development of a confirmed myelodysplastic syndrome or other clonal blood disorder should be reported as an SAE and full reports must be provided by the investigator to AstraZeneca Patient Safety. Olaparib treatment should be discontinued if subject's diagnosis of MDS and/or AML is confirmed.

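### Section 8.3.2 makes it optional to tell the sponsor of a known, related SAE learned of after the last visit, and the clause can reach into the 28-day window that is summarised

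*Protocol*

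**What the plan says.** Protocol 8.3.2 collects AEs from consent "until 28 days after last olaparib dose in Treatment Phase and Follow-up Phase". It requires each SAE, and any update to one, to reach the sponsor within 24 hours. It then turns to people who have finished: "Investigators are not obligated to actively seek AE or SAE in former study subjects". If an investigator nevertheless learns of an SAE or a death after the last visit, and thinks it reasonably related to treatment or participation, "the investigator may notify the sponsor". No time limit is attached.

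Other places that bear on this:

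- **8.4.1:** "All SAEs have to be reported, whether or not considered causally related to the study drug". Its 24-hour duty opens with "If any SAE occurs in the course of the study".
- **6.7:** subjects on olaparib at the end of the Treatment Phase "may continue to receive olaparib, if in the opinion of their treating physician they are continuing to derive clinical benefit", supplied through a separate compassionate use program. "These subjects shall not be actively monitored for AE's". The same sentence makes the treating physician responsible for getting all SAEs to the relevant authorities. The sponsor is not named as a recipient.
- **8.4.5.3:** a diagnosis of MDS, or of another clonal disorder of the blood, once confirmed, "should be reported as an SAE and full reports must be provided by the investigator to AstraZeneca Patient Safety". The section title limits it to toxicity on study treatment, but the sentence itself sets no time limit.
- **9.4.2:** AEs within 28 days of the last dose enter the summaries. Those that follow further cancer therapy are flagged, not removed.
- **1.1 and 4.1:** the Follow-up Phase is for subjects who stop early. It lasts 28 days or until other treatment starts, if that is sooner.

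**The concern.** Not asking sites to search for events in former subjects is a normal limit on workload. This clause goes further. It applies only after the investigator already knows of a serious event and has already attributed it to the drug, and it then leaves passing the information on to discretion. During the study, even unrelated SAEs must be sent within a day. The events under the weakest rule are therefore known, serious and judged related.

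Safety is the trial's only objective (Section 3), and Appendix A 5 relies on the sponsor's representatives and Patient Safety to watch for problems. They can act only on what reaches them. A second issue is completeness of the counted data. If the last visit can precede the end of the 28-day window, the optional rule applies to events that 9.4.2 means to summarise.

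**Working it through.** The protocol gives no figure on this point, so the check is mainly a comparison of passages.

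**1. Who must be told, and when**

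| Situation | Section | Recipient | Duty |
|---|---|---|---|
| SAE in the course of the study | 8.3.2, 8.4.1 | Sponsor | Mandatory, 24 hours |
| Related SAE learned of after the last visit | 8.3.2 | Sponsor | Optional, no timeline |
| Any SAE in a subject continuing olaparib | 6.7 | Relevant authorities | Treating physician's responsibility |
| Confirmed MDS or other clonal disorder | 8.4.5.3 | Patient Safety | Full reports mandatory; titled for on-treatment toxicity; no time limit |

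Only the second row lacks a duty. The third row is a real duty, but it does not name the sponsor. Whether the fourth covers a diagnosis confirmed after the last visit cannot be settled from the text.

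**2. Can the optional clause apply inside the 28-day window?**

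The clause starts at the last visit. The window in 8.3.2 and 9.4.2 ends 28 days after the last dose. They coincide only if every subject has a contact at the end of the window.

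- *Early discontinuer who starts new treatment.* Under 1.1 and 4.1, follow-up ends when the new treatment starts. As an illustration, if that is day 10 after the last dose, 28 − 10 = 18 days of the window lie after the end of follow-up. 9.4.2 clearly intends to count this period, since it flags such events and keeps them.
- *Subject who completes Day 182.* If follow-up is only for early discontinuers, the last visit is about Day 182 and up to 28 days of the collection window in 8.3.2 lie beyond it.
- *Limit on this.* Sections 1.1 and 4.1 also describe a telephone contact 28 days after the End-of-Treatment Visit. If every subject gets that call, the overlap for completers largely closes. The text does not agree on who receives it.

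For these subjects, one sentence of 8.3.2 requires collection and another makes notification optional.

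**3. How many subjects might be on olaparib after the Treatment Phase?**

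The protocol says only that they may continue. A rough range, assuming exponential progression-free survival:

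- Time: 182 / 30.4375 = 5.98 months.
- Formula: S = exp(−ln 2 × 5.98 / median).
- Medians in the protocol: 19.1 months (SOLO-2) and 8.4 months (Study 19) for ovarian cancer; 7 months (OlympiAD) for breast cancer.
- Results: 80.5%, 61.1% and 55.3% progression-free.
- With the SOLO-2 median: 160 × 0.805 + 40 × 0.553 = 151 of 200 (75%).
- With the Study 19 median: 160 × 0.611 + 40 × 0.553 = 120 of 200 (60%).
- If a further 20% stop for other reasons (assumed; range 0 to 20%): 151 × 0.8 = 121 (60%) and 120 × 0.8 = 96 (48%).

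The range is about 48 to 75%.

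**4. Effect on the sample size**

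None. The figure of approximately 190 in 9.2 follows from 1.96² × 0.40 × 0.60 / 0.07² = 188.2, rounded up to 189, and does not depend on this clause.

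**The case against.** The strongest reply is that the rules govern different periods and do not conflict. The duty in 8.4.1 is for SAEs in the course of the study, 8.4.5.3 is titled for toxicity on study treatment, and the 8.3.2 clause is for former subjects. This stands. A reader might infer that 8.4.5.3 makes reports of late marrow disorders mandatory and so contradicts 8.3.2. The text does not say so: onset after the study is not mentioned. What can be said is that the relation is unclear, because the reporting sentence has no time limit.

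A second reply is that these events do not go unreported. Section 6.7 gives the treating physician a duty covering all SAEs, which is wider than 8.3.2 because it is not limited to related ones. Sections 7.1, 8.3.9 and 8.3.10 also direct serious events at Indian sites to the regulator and ethics committees, although within text on progression and disease symptoms. This stands too, and it narrows the point to the route to the sponsor. Nor can the 8.3.2 clause be called the main route for late events: the compassionate use program's own reporting terms are not in the protocol.

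A third reply is that late events lie outside the planned summaries, so no estimate changes. That is true beyond 28 days. It does not hold for the overlap shown in step 2 of the working, and it does not answer why a known, related death may be withheld from the sponsor.

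**Conclusion.** The point holds as a defect in the wording of 8.3.2: sponsor notification of a known, related SAE after the last visit is optional and has no timeline, and the clause can cover events inside the 28-day window. It is worth correcting because safety is the only objective, but it does not undermine the design. The number of events affected cannot be derived from the protocol. The in-window part rests on reading 1.1 and 4.1 as ending follow-up at new treatment or at Day 182, and it shrinks if the 28-day call is made to everyone.

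Three stronger readings are not supported:

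- *Most subjects will continue olaparib.* This is an inference. The range of 48 to 75% rests on exponential progression-free survival and assumed other stopping, and its lower end is below half.
- *The loss falls especially on late MDS/AML and pneumonitis.* The protocol lists these as exclusion and discontinuation conditions but gives no latency or late-onset rate.
- *One missed late case would overturn an upper limit of 3/200 = 1.5% for an event not seen in 200 subjects.* An event after the 28-day window does not enter that count, so the limit would not move.

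**What to change.** In 8.3.2, replace the optional wording with: *must notify the sponsor within 24 hours of awareness*. This matches the timeline already used in 8.3.2 and 8.4.1. The sentence that no active search is required can stay.

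Add to 9.4.2 that events within 28 days of the last olaparib dose remain in the AE summaries whether or not they came to light after the last visit. Later related SAEs received up to database lock should be listed separately, outside the incidence tables. Database lock gives a definite cut-off; Table 2 places it in December 2021, after a last visit in October 2021.

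Reconcile 8.4.5.3 with 8.3.2 by stating whether its reporting duty applies to diagnoses confirmed after the last visit, and cross-refer from 6.7 so that the sponsor's place in the reporting route is clear.

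The cost is a few additional safety reports, one extra listing and the wording changes. No visits, samples or active follow-up are added.

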8.3.3 Follow-up of AEs and SAEs

After the initial AE/SAE report, the investigator is required to proactively follow each subject at subsequent visits/contacts. All SAE's will be followed until resolution, stabilization, the event is otherwise explained, or the subject is lost to follow-up.

Any AEs that are unresolved at the subject's last AE assessment in the study are followed up by the Investigator for as long as medically indicated, but without further recording in the CRF. AstraZeneca retains the right to request additional information for any subject with ongoing AE(s)/SAE(s) at the end of the study, if judged necessary.

8.3.4 Adverse event data collection

The following variables will be collect for each AE;

- AE (verbatim)
- The date when the AE started and stopped
- Intensity and change in intensity of the AE
- CTCAE grade and changes in the CTCAE grade
- Whether the AE is serious or not
- Investigator causality rating against the Study Drug (yes or no)
- Action taken with regard to Study Drug
- AE caused subject's withdrawal from study (yes or no)
- Outcome.

In addition, the following variables will be collected for SAEs:

- Date AE met criteria for serious AE
- Date Investigator became aware of serious AE
- AE is serious due to
- Date of hospitalisation
- Date of discharge
- Probable cause of death
- Date of death

- Autopsy performed
- Causality assessment in relation to Study procedure(s)
- Causality assessment to other medication'

8.3.5 Causality collection

The Investigator will assess causal relationship between study drug and each Adverse Event, and answer 'yes' or 'no' to the question 'Do you consider that there is a reasonable possibility that the event may have been caused by the study drug?'

For SAEs, causal relationship will also be assessed for other medication and study procedures. Note that for SAEs that could be associated with any study procedure the causal relationship is implied as 'yes'.

A guide to the interpretation of the causality question is found in Appendix B to the Clinical Study Protocol.

8.3.6 Adverse events based on signs and symptoms

All AEs spontaneously reported by the subject or care provider or reported in response to the open question from the study site staff: '*Have you had any health problems since the previous visit?*' or revealed by observation will be collected and recorded in the CRF. When collecting AEs, the recording of diagnoses is preferred (when possible) to recording a list of signs and symptoms. However, if a diagnosis is known and there are other signs or symptoms that are not generally part of the diagnosis, the diagnosis and each sign or symptom will be recorded separately.

8.3.7 Adverse events based on examinations and tests

The results from the Clinical Study Protocol mandated laboratory tests and vital signs will be summarised in the CSR. Deterioration as compared to baseline in protocol-mandated laboratory values, vital signs as in section 8.2 should therefore only be reported as AEs if they fulfil any of the SAE criteria or are the reason for discontinuation of treatment with the study drug.

If deterioration in a laboratory value/vital sign is associated with clinical signs and symptoms, the sign or symptom will be reported as an AE and the associated laboratory result/vital sign will be considered as additional information. Wherever possible the reporting Investigator uses the clinical, rather than the laboratory term (e.g., anaemia versus low haemoglobin value). In the absence of clinical signs or symptoms, clinically relevant deteriorations in non-mandated parameters should be reported as AE(s).

Deterioration of a laboratory value, which is unequivocally due to disease progression, should not be reported as an AE/SAE.

Any new or aggravated clinically relevant abnormal medical finding at a physical examination as compared with the baseline assessment will be reported as an AE unless unequivocally related to the disease under study, see sections 8.3.9 and 8.3.10.

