6.6 Dose modification

This protocol allows for some alteration from the currently outlined dosing schedule, but the maximum daily dose shall not exceed 300 mg BD. Dose modifications are permitted in case of AE's as per section 8.4.6.

In case a dose reduction is necessary, the Study treatment will be administered as follows:

Table 5: Dose Reduction Schedule

Initial dose	Following re-challenge post interruption: Dose reduction 1	Dose reduction 2
300 mg twice daily	250 mg Twice daily	200 mg twice daily (lowest allowable dose level)

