8.4.5.2 Management of neutropenia, leukopenia and thrombocytopenia

Table 8 Management of neutropenia, leukopenia and thrombocytopenia

Toxicity	Study treatment dose adjustment
CTCAE Grade 1-2	Investigator judgement to continue treatment or if dose interruption, this should be for a maximum of 4 weeks; appropriate supportive treatment and causality investigation
CTCAE Grade 3-4	Dose interruption until recovered to CTCAE gr 1 or better for a maximum of 4 weeks. If repeat CTCAE grade 3-4 occurrence, dose reduce to 250 mg twice daily as a first step and 200 mg twice daily as a second step

Adverse event of neutropenia and leukopenia should be managed as deemed appropriate by the investigator with close follow up and interruption of study drug if CTC grade 3 or worse neutropenia occurs.

Primary prophylaxis with Granulocyte colony-stimulating factor (G-CSF) is not recommended, however, if a subject develops febrile neutropenia, study treatment should be stopped and appropriate management including G-CSF should be given according to local hospital guidelines. Please note that G-CSF should not be used within at least 24 h (7 days for pegylated G-CSF) of the last dose of study treatment unless absolutely necessary.

Platelet transfusions, if indicated, should be done according to local hospital guidelines.

For cases where subjects develop prolonged haematological toxicity (\geq 2 weeks interruption/delay in study treatment due to CTC grade 3 or worse), refer to Section 8.4.5.3.

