8.4.6 Management of Non – hematological toxicity

Repeat dose interruptions are allowed as required, for a maximum of 4 weeks on each occasion. If the interruption is any longer than this the study monitor must be informed. Where toxicity reoccurs following re-challenge with study treatment, and where further dose interruptions are considered inadequate for management of toxicity, then the subject should be considered for dose reduction or must permanently discontinue study treatment.

Study treatment can be dose reduced to 250 mg bd as a first step and to 200 mg bd as a second step. Treatment must be interrupted if any NCI-CTCAE grade 3 or 4 adverse event occurs which the investigator considers to be related to administration of study treatment.

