9. STATISTICAL CONSIDERATIONS

9.1 Statistical hypotheses

There is no formal sample size calculation as this study is being conducted as a regulatory requirement for a phase IV study including Indian subjects in the approved indications post marketing of olaparib. The primary endpoint is to demonstrate the safety profile of olaparib in routine clinical practice as assessed by the incidence of AEs (serious and non-serious) observed during trial.

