9.2 Sample size determination

Based on the results of OlympiAD and SOLO – 2 trials of Olaparib tablets in platinum sensitive, relapsed ovarian cancer patients with BRCA1/2 mutation and in gBRCAm positive metastatic breast cancer, the incidence rate of the any adverse event (mentioned as part of the labelling information of Olaparib) of severity grade 3 or higher was observed to be approximately 40%. This value of the incidence rate of interest has been used for the sample size estimation in this study.(Pujade-Lauraine et al., 2017; Robson et al., 2017)

Assuming the true incidence rate of any adverse event (mentioned as part of the labelling information of Olaparib) of severity grade 3 or higher to be 40%, corresponding data from approximately 190 Indian adult patients satisfying the protocol specified eligibility criteria will be required in this study for estimating the sample (study based) incidence rate with 7% error margin and using 95% confidence interval. In this study, we expect to recruit 160 patients from platinum sensitive relapsed ovarian cancer and 40 patients from gBRCAm positive metastatic breast cancer as per the Indian HA approved indication to satisfy the Lynparza MA conditional approval.

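### Under section 8.3.7, an asymptomatic, non-serious grade ≥3 laboratory abnormality that leads only to a dose interruption or reduction gets no AE entry and no causality answer

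*Protocol*

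**What the plan says.** Section 8.3.7 covers abnormalities found by tests. Because mandated laboratory results and vital signs will be summarised in the study report, their deterioration "should therefore only be reported as AEs if they fulfil any of the SAE criteria or are the reason for discontinuation of treatment" with study drug. If there are symptoms, the sign or symptom is the AE and the laboratory value is supporting information. The route for findings without symptoms covers non-mandated parameters only. Section 8.2.1 names 8.3.7 as the rule for laboratory-based AEs, and its Table 6 mandates haemoglobin, leukocytes with differential, platelets, creatinine, bilirubin and liver enzymes.

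Section 9.1 describes the primary endpoint as the safety profile "as assessed by the incidence of AEs (serious and non-serious) observed during trial". Section 9.2 takes the true incidence of any labelled adverse event "of severity grade 3 or higher to be 40%, corresponding data from approximately 190 Indian adult patients" being needed for a 7% margin with a 95% confidence interval. Section 8.3.5 asks the yes/no causality question of each adverse event.

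Other sections describe events that lead to dose changes as adverse events:

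- Section 6.6: "Dose modifications are permitted in case of AE's as per section 8.4.6".
- Section 8.4.5.2: "Adverse event of neutropenia and leukopenia should be managed as deemed appropriate by the investigator".
- Section 8.4.6: "Treatment must be interrupted if any NCI-CTCAE grade 3 or 4 adverse event occurs which the investigator considers to be related" to study treatment.
- Section 8.3.4 collects, for each AE, "Action taken with regard to Study Drug".

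**The concern.** Safety is the study's only objective. Tables 7 and 8 expect grade 3 or worse blood counts to lead to interruption and, in defined circumstances, reduction. Those are the events 8.3.7 leaves out when the patient has no symptoms, no seriousness criterion is met and treatment is not stopped for good. A site that follows 8.3.7 exactly enters the value in the laboratory data and the interruption in the dosing data, but completes no AE form.

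Three things follow. The recorded grade ≥3 AE frequency, and the AE frequencies of cytopenias and liver-test abnormalities, can only be understated. The causality answer is never collected, and no analysis plan can recover it later. And sites that read 6.6, 8.4.5.2 or 8.4.6 as implying an AE entry will record the same event differently from sites that follow 8.3.7.

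**Working it through.** **The plan's own figure.** Inputs from section 9.2: p = 0.40, margin d = 0.07, 95% confidence.

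n = 1.96² × p(1 − p) / d² = 1.96² × 0.40 × 0.60 / 0.07² = 188.2, which agrees with the stated figure of about 190. The half-width at p = 0.40 is 6.97 points for n = 190 and 6.79 points for n = 200. The sample size is not in question; the issue is which events are counted.

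**Which events escape.** Take an asymptomatic grade 3 platelet count that leads to a short interruption and then recovers:

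1. Symptoms (8.3.7): none, so no symptom AE.
2. SAE criterion (Appendix B 2, B 5): not met, unless the investigator judges it an important medical event.
3. Discontinuation: no.
4. Asymptomatic route in 8.3.7: not open, because platelets are a mandated parameter.
5. Result: no AE entry, hence no 8.3.5 causality answer.

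An isolated grade 3 transaminase rise follows the same path. It also meets 8.4.6, which makes interruption depend on a related grade 3 or 4 adverse event, while 8.3.7 gives the finding neither AE status nor a recorded relatedness answer.

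**Illustration of size.** The protocol does not give the share of grade ≥3 events that would go unrecorded, so that share is assumed. Let a be the proportion of subjects with grade ≥3 anaemia and f the share of them whose only grade ≥3 event is unrecorded. The recorded grade ≥3 rate is then 0.40 − a × f. Section 2.1 gives a = 0.06 from the placebo-controlled phase II capsule study, the one cited rate from a maintenance setting.

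| f (assumed) | Drop a × f | Recorded rate | Subjects, 200 × a × f |
|---|---|---|---|
| 10% | 0.6 points | 39.4% | 1.2 |
| 25% | 1.5 points | 38.5% | 3 |
| 50% | 3.0 points | 37.0% | 6 |
| 100% (ceiling) | 6.0 points | 34.0% | 12 |

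Even the ceiling is below 7 points; reaching the margin would need f = 0.07 / 0.06 = 1.17, which is impossible. The protocol gives no grade ≥3 rates for neutropenia, thrombocytopenia or liver enzymes, so their contribution is not quantified.

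**Proportion with any AE.** A subject counts once, and section 8.4.6.2 cites nausea alone at 71% in one study. Nearly every affected subject would probably have some other AE, so this proportion would barely change.

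**The case against.** The strongest defence is that 8.3.7 is a deliberate convention with a stated reason: mandated laboratory results are summarised separately, so they need not be repeated as AEs. Section 3 lists haematology and chemistry among the safety variables, and section 8.4.6.3 has all dose changes recorded with reasons. This stands. The data are not lost; what is missing is the AE entry, its causality answer and its place in the AE tables.

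The gap is also narrowed elsewhere. Anaemia or neutropenia needing transfusion is an example in Appendix B 5 of an event usually considered serious, and Table 7 names transfusion as a possible treatment at Hb below 8 g/dl, so f may be small for anaemia. Sections 7.1 and 8.4.5.3 lead from prolonged holds or non-recovery to discontinuation, which does trigger AE reporting. Hy's Law cases have their own route. What remains is mainly short, asymptomatic, untransfused episodes that recover.

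The cross-references vary in weight: 6.6 is permissive, 8.4.6 concerns non-haematological toxicity, and the action-taken field serves any AE. They show a poor fit that needs reconciling. They do not show that 8.3.7 is overridden. Grade ≥3 incidence is a sizing quantity in 9.2 and is not itself listed as an endpoint in section 3. The study is descriptive, so no test is affected.

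Two stronger readings are tempting. A reader might infer that 8.3.7 contradicts Appendix B 1, which allows an abnormal laboratory finding to be an AE. But B 1 is a general definition and 8.2.1 points to 8.3.7 as the specific rule. A reader might also infer that the bias could use up the 7-point margin, by taking the 20% grade ≥3 anaemia rate in section 2.1. That rate comes from third-line-or-later treatment of ovarian cancer, in a study whose overall grade ≥3 rate was 55%. Inclusion criteria 4 and 5 do not admit that indication, and the rate should not be set against the 40% that 9.2 takes from other trials.

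The analysis plan, not shown here, could grade laboratory values by CTCAE. It cannot supply causality answers that were never asked for.

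**Conclusion.** The point holds in limited form and should be fixed. Followed exactly, 8.3.7 leaves asymptomatic, non-serious grade ≥3 laboratory abnormalities that lead only to a dose change without an AE entry or a causality answer. The direction is certain: recorded grade ≥3, cytopenia and liver-test AE frequencies can only be too low. The size cannot be derived from the protocol. For anaemia alone it is 0.6 to 3.0 points, about 1 to 6 of 200 subjects, and it cannot reach the 7-point margin. This rests on the 40% assumption in 9.2, a 6% rate from a capsule study carried over to tablets, and an assumed unrecorded share of 10% to 50%. Confidence in the size is low, because other cytopenias and liver tests are unquantified. The causality gap is the firmer part of the finding and needs no assumed rate.

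**What to change.** In 8.3.7, also record as an AE any deterioration in a mandated laboratory value that is CTCAE grade ≥3 or that led to dose interruption or reduction. The causality answer then follows under 8.3.5, and 8.3.7 agrees with 6.6, 8.4.5.2 and 8.4.6. The cost is a wording change, matching CRF guidance, more AE entries per site and a slightly less favourable AE figure.

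If 8.3.7 is kept, report the grade ≥3 incidence so that a subject counts when either the AE form or the CTCAE-graded laboratory data shows the event, and state that laboratory-only events carry no causality rating. This costs one derived variable from data already collected, but leaves the causality gap open.

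Neither route changes a dose or a management rule.
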